8.3.4 Outcome

The investigator will follow-up the AE and SAE until resolution or until no further medically relevant information can be expected. AE and SAE outcome will be classified as follows:

- Continuing/ongoing
- Resolved
- Resolved with sequelae
- Permanent
- Fatal

9 STATISTICAL CONSIDERATIONS

9.1 Sample size justification

The target population for this study will be adult Cambodians who work and sleep in the forest (farmers, collect forest goods, hunting, etc.). 2,200 study participant episodes are required in each arm to have sufficient power to detect a statistically significant difference between the treatment arm and a control arm. The estimate of the required sample size is complicated by the scarce data on *P. falciparum* incidence in forest workers. We estimate the required sample size based on our study in forest rangers in Vietnam in 2016 (13) combined with an estimate of the time spent in the forest from ongoing studies in northeast Cambodia. In Viet Nam, we found that 1 forest ranger became infected per 500 person-nights spent in the forest. We estimate conservatively that during each episode, each participant will spend at least 10 days in a high-risk zone. We will need 20 infectious bites per study-arm: $2 \times 20 = 40$ (i.e. irrespective of protection afforded per arm). Risk days/nights needed: $40 \times 500 = 20,000$. Each participant episode contributes 10 risk days/nights: $20,000/10 = 2,000$ episodes required. The assumed loss to follow-up could be as high as 10% =200. Therefore, the total sample required is $2,000+200=2,200$ study participant episodes.

Formally, we anticipate that the risk of being Pf positive without receiving prophylaxis will be around 5%. A total of 1,605 participant-episodes per arm are enough to detect a difference of at least 40% in the proportion of episodes with a Pf positive result as defined by the 28-day PCR parasite positivity rate i.e. from 5% positivity in participants without receiving antimalarial prophylaxis (i.e. multivitamin) to 3% positivity in participants receiving artemether-lumefantrine prophylaxis. This has been estimated with 80% power and 5% significance level. However, we also anticipate that we will likely observe multiple episodes being recruited into the study that can reduce power of the study if not accounted for. To compensate for the multiple episodes and any losses to follow up, we plan to recruit approximately 600 (i.e. 595) additional episodes in each group on top of the required 1605 single episodes. This gives an additional 27% episodes to account for the multiple episodes and losses to follow up. Thus, the overall sample size will be 4,400 episodes (i.e. 2,200 episodes in the treatment arm and 2,200 episodes in the control arm). The sample size calculations have been performed in Stata version 15.

9.2 Statistical Analyses

Analysis of other endpoints will be described in a Statistical Analysis Plan. A brief overview is given below.

9.2.1 Proportions

These will be compared using chi squared or Fisher's exact test, as appropriate. Crude proportions will be calculated with the exact 95% confidence intervals (CI), where relevant.

9.2.2 Continuous data

These will be summarised by medians (IQR, ranges) and means (standard deviations, 95% CIs), as appropriate, and will include the parasite counts and laboratory parameters. Comparisons of continuous data will be assessed using the paired/unpaired t tests or the sign rank/Mann Whitney U tests, as appropriate.

9.2.3 Safety analysis

Safety analyses will be based on the whole population that get administered the study drug. Safety and tolerability of ACT versus multivitamin will be assessed by comparing the frequency (%) of adverse events and serious adverse events, with particular attention to abdominal pain, appetite perturbation, using the Fisher's exact test. Safety data will be presented in tabular and/or graphical format and summarised descriptively. Any clinically relevant abnormalities or values of potential clinically concern will be described. Participants will be analysed according to an intention to treat and a per protocol method where appropriate.

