8. SAFETY REPORTING

This trial will use drugs that have either been registered or evaluated extensively. To add to the evidence base for safety of AL as prophylaxis, we will record and review all Adverse Events (AEs) and Serious Adverse Events (SAEs) that are reported to occur in the study.

A symptom questionnaire will be performed on enrolment and at each subsequent follow-up visit to the health care center, to aid in the identification of adverse events. In addition, enrolled individuals will be encouraged to promptly report any unexpected symptoms or illnesses between follow-up visits to the study team.

The investigator is responsible for the detection and documentation of events meeting the criteria and definition of an adverse event (AE) or serious adverse event (SAE), as provided in this protocol.

All SAEs and AEs will be promptly documented from the moment of drug administration in the study to discontinuation of the participant from study participation. Any events occurring between screening and drug administration will be considered as baseline, preexisting conditions.

All adverse events must be recorded in the AE/SAE CRF. To avoid colloquial expressions, the adverse event should be reported in standard medical terminology. Whenever possible, the adverse event should be evaluated and reported as a diagnosis rather than as individual signs or symptoms. If a definitive diagnosis is not possible, the individual symptoms and signs should be recorded. Whenever possible, the aetiology of the abnormal findings will be documented on the CRF. Any additional relevant laboratory results obtained by the Investigator during the course of this study will be recorded on the CRF.

If the event meets the criteria for “serious”, the SAE must be reported to the PAL-Cambodia safety team within 24 hours from the time that the event was identified. If further data is required, additional documentation can be submitted. All SAEs must be followed until resolution, or until the SAE is deemed permanent or leads to death.

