4.3 ANALYSIS OF PRIMARY OUTCOME

Primary objective:

To compare the efficacy of the ACT artemether-lumefantrine versus a multivitamin preparation as defined by the 28-day PCR parasite positivity rate or incidence of confirmed clinical malaria of any species

Primary endpoints:

Composite endpoint

- 1. 28-day PCR Plasmodium positivity rate of any species or
- 2. Proportion of participants with confirmed clinical malaria of any species reported between day 0 and day 28

The main analysis strategy for the primary outcome will be the intention-to-treat (ITT) principle followed by the per protocol (PP) analysis. Thus, we will first analyse the ITT population in which all participants recruited in the trial will be included in the analysis according to the randomisation arm irrespective of what they actually got. These ITT analyses will be followed by the analysis of the per protocol (PP) population in which, participants who did not adhere to the protocol will be excluded from analysis.

The efficacy of the ACT artemether-lumefantrine versus a multivitamin preparation as defined by the 28-day PCR parasite positivity rate or incidence of confirmed clinical malaria analysis in each arm will be summarised using proportions and the 95% confidence intervals. Crude proportions will be calculated with the exact binomial 95% confidence intervals. The risks differences in efficacy between AL and multivitamin will be reported along with the corresponding 95% confidence intervals. The robust standard error will be used to adjust for intracluster correlation of episodes from the same individual. The mixed effects Poisson/negative binomial regression model will be used to model the adjusted incidence rate ratios (IRR). The mixed effects models will take into account the correlation of multiple episodes from same participant.

Tests of significance will be performed at 5% significance level.

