#### 4.4.5 Adverse events and serious adverse events by study arms during the course of prophylaxis.

Adverse events will be graded according to Common Terminology Criteria for Adverse Events (CTCAE) Version 5.0 November 2017.

All adverse event summaries will refer to treatment emergent adverse events, i.e. adverse events that newly started or increased in intensity after the study drug administration. AE summaries will be generated for all AEs that occurred after study drug administration, until the end of the study.

Incidence of adverse events and serious adverse events by study arms during the course of prophylaxis will be presented in the table 6a below. AE intensity and relationship to study drug wil be presented as in tables 6b and 6c. Graphical presentations might be considered when presenting these.

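### Harms are compared between arms only by percentages and a Fisher p-value; a risk difference with a 95% confidence interval should be added to SAP Table 6a

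*Protocol*

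**What the plan says.** Protocol 9.2.3 sets the method: "Safety and tolerability of ACT versus multivitamin will be assessed by comparing the frequency (%) of adverse events and serious adverse events". The test it names is Fisher's, and it singles out two symptoms, pain in the abdomen and disturbed appetite. The population is wide: "Safety analyses will be based on the whole population that get administered the study drug". The same section adds that "Safety data will be presented in tabular and/or graphical format and summarised descriptively".

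SAP 4.4.5 carries this out: "Incidence of adverse events and serious adverse events by study arms during the course of prophylaxis will be presented in the table 6a below". Table 6a has three result columns: n (%) for AL, n (%) for multivitamin, and a p-value. Its rows are 13 symptoms and one line for SAEs. Tables 6b and 6c break the same symptoms down by severity and by relationship to study drug within each arm, without a comparison.

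For efficacy the SAP goes further (section 4.3): "The risks differences in efficacy between AL and multivitamin will be reported along with the corresponding 95% confidence intervals". Tables 2 and 3 have a column for it.

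The nearest thing to an interval for harms is the general rule in Protocol 9.2.1: "Crude proportions will be calculated with the exact 95% confidence intervals (CI), where relevant". That covers each arm's proportion separately, not the difference between arms.

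**The concern.** Protocol section 8 gives a purpose for collecting adverse events: "To add to the evidence base for safety of AL as prophylaxis". AL would be taken repeatedly, for up to 112 days (Protocol 6.6), by people enrolled without confirmed clinical malaria. The useful safety result is therefore an estimate of the excess of harm and the largest excess that the data leave open. A p-value gives neither.

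The sample size was set for efficacy (5% v 3% PCR positivity), and no background harm rate or power for harms is stated. If SAEs are rare, a non-significant p-value is likely even when AL raises their rate. Without an estimate and interval beside it, Table 6a makes that result easy to over-read.

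**Working it through.** **1. Inputs.** From the documents: 2,200 episodes per arm planned and 1,605 before inflation (Protocol 9.1, SAP 2.5); 5% significance level (SAP 4.3); Fisher's exact test (Protocol 9.2.3). Assumed: a two-sided test, independent episodes, and the control event rates, because the documents give no adverse event or SAE rate.

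**2. The plan's own figure.** For 5% v 3%, 80% power and two-sided 5%, with mean proportion 0.04:

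n = [1.960 × √(2 × 0.04 × 0.96) + 0.842 × √(0.05 × 0.95 + 0.03 × 0.97)]² / 0.02² ≈ 1,506.

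With the continuity correction, n' = (n/4) × [1 + √(1 + 4/(n × 0.02))]² ≈ 1,605. The stated figure reproduces. It concerns efficacy only.

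**3. Chance of missing a true doubling of SAEs.** Miss rate = 1 − Σ P(x; n, 2p) × P(y; n, p), where P is the binomial probability and the sum runs over all pairs of counts (x on AL, y on multivitamin) with Fisher p ≤ 0.05. This is exact enumeration.

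| Assumed control rate p | AL rate 2p | Expected control SAEs (2,200) | Missed, 2,200 per arm | Missed, 1,605 per arm |
|---|---|---|---|---|
| 0.2% | 0.4% | 4.4 | 85% | 90% |
| 0.3% | 0.6% | 6.6 | 76% | 83% |
| 0.5% | 1.0% | 11.0 | 58% | 70% |
| 0.6% | 1.2% | 13.2 | 50% | 63% |
| 1.0% | 2.0% | 22.0 | 25% | 40% |
| 2.0% | 4.0% | 44.0 | 3% | 10% |

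The miss rate crosses 50% at a control rate of about 0.59% with 2,200 per arm and about 0.81% with 1,605. Either way this is about 13 expected control events.

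**4. Common symptoms** (2,200 per arm, rates again assumed). The miss rate is 59% for 3% to 4%, 28% for 3% to 4.5%, 22% for 5% to 7%, 45% for 10% to 12%, and 13% for 10% to 13%.

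**5. What an interval adds.** Take hypothetical counts of 12 SAEs on AL and 5 on multivitamin, each of 2,200.

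- Proportions: 12/2,200 = 0.545% and 5/2,200 = 0.227%; difference d = +0.318 points. Fisher p = 0.14.
- Wilson 95% limits: AL 0.312% to 0.951%; multivitamin 0.097% to 0.531%.
- Newcombe lower limit: 0.318 − √[(0.545 − 0.312)² + (0.531 − 0.227)²] = −0.06 points.
- Newcombe upper limit: 0.318 + √[(0.951 − 0.545)² + (0.227 − 0.097)²] = +0.74 points.

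Table 6a as drawn would print 12 (0.5), 5 (0.2) and p = 0.14. The interval adds that an excess of about 7 SAEs per 1,000 episodes is not excluded.

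**The case against.** The strongest reply is that the plan draws no conclusion of no harm. Adverse event incidence by arm is a secondary endpoint, reported with per-arm counts, severity, relatedness and descriptive summaries, and each SAE is individually reported, assessed for causality and followed up. Table 6a would show 12 v 5 openly, and a reader could work out the difference and its interval from the counts. All of this stands. It limits the point to the form of the between-arm inference: the counts are there, but the plan commits the trial to a p-value and not to an estimate with its precision.

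Three stronger readings are tempting and are not supported:

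- *The plan treats a non-significant test as proof of safety.* Neither document says so, and no non-inferiority claim for harms is planned. A missing margin or missing power for harms is therefore not itself a defect.
- *The test misses a doubling of SAEs more often than not.* That depends on a rate the documents do not give. It is true only below about 0.6% of episodes with 2,200 per arm; at 2% the test detects a doubling 97% of the time.
- *Harms are the only comparison given a bare p-value.* SAP Table 5 does the same for travel and risk behaviour. Nor does Table 4 serve as a contrast: its risk difference compares mutant with wild type within each arm, not AL with multivitamin. The fair contrast is with the efficacy results in Tables 2 and 3.

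It is also fair to object that a simple interval treats episodes as independent. One person can be enrolled, and re-randomised, up to three times (Protocol 6.6), and the SAP's robust standard errors are written for the primary outcome. Fisher's test has the same weakness. The fix has to deal with this.

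**Conclusion.** The point holds as a cheap improvement. The only planned between-arm inference on harms is a p-value, and no section supplies an estimate or interval for the AL minus multivitamin difference. That gap exists whatever the SAE rate turns out to be.

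Its practical size does depend on the rate. A true doubling would be missed 85% of the time at a control rate of 0.2%, but 25% of the time at 1%. These figures rest on assumed control rates, a two-sided 5% test and 2,200 independent episodes per arm. The documents give no within-person correlation with which to adjust them.

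**What to change.** In SAP Table 6a, add a column with the AL minus multivitamin risk difference and its 95% confidence interval for each symptom and for SAEs. Use robust standard errors clustered on the participant, as SAP 4.3 does for efficacy. For sparse rows such as SAEs, use a Newcombe or exact interval and state that it assumes independent episodes.

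Keep the Fisher p-value as descriptive. State in SAP 4.4.5 and Protocol 9.2.3 that safety is interpreted from the estimate and its upper confidence limit, and that a non-significant p-value is not evidence of no harm.

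The cost is one table column, a short statement in the SAP and matching wording in the protocol; no new data or participants are needed. The downside is that wide intervals for rare events will make the safety statement look less favourable.

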9.2.4 Adverse events

Adverse events will be graded according to Common Terminology Criteria for Adverse Events (CTCAE) Version 5.0 November 2017.

All adverse event summaries will refer to treatment emergent adverse events, i.e. adverse events that newly started or increased in intensity after the study drug administration. AE summaries will be generated for all AEs that occurred after study drug administration, until the end of the study.

10 DIRECT ACCESS TO SOURCE DATA/DOCUMENTS

Direct access will be granted to authorised representatives from the sponsor and host institution, the regulatory authorities, and ethical committee (if applicable), to permit trial-related monitoring and inspections.

11 QUALITY CONTROL AND QUALITY ASSURANCE PROCEDURES

The study will be conducted in accordance with the current approved protocol, ICH GCP, any national regulations that may apply to this study and standard operating procedures. The WWARN will be engaged in assuring QA/QC of study execution in collaboration with the MORU Clinical Trials Support Group (CTSG). Their role will include but not be limited to monitoring adherence to SOPs for collection of laboratory specimens and quality checks (curation) of laboratory data according to standard methodologies.

11.1 Monitoring

Study sites may have in place a system for internal monitoring. In addition, regular external monitoring of all sites will be performed by the MORU CTSG according to ICH GCP and a Monitoring Plan. Data will be evaluated for compliance with the protocol and accuracy in relation to source documents. The monitors will check whether the clinical trial is conducted and data are generated, documented and reported in compliance with the protocol, GCP and the applicable regulatory requirements. Evaluation of on-site monitoring schemes, such as a reciprocal monitoring scheme, may be undertaken at selected sites by CTSG.

12 ETHICS

12.1 Declaration of Helsinki

The Investigator will ensure that this study is conducted in compliance with the current revision of the Declaration of Helsinki (Fortaleza 2013).

12.2 ICH Guidelines for Good Clinical Practice

The Investigators will ensure that this study is conducted according to any National Regulations and that it will follow the principles of the ICH Guidelines for Good Clinical Practice.

12.3 Approvals

The study protocol and its associated documents will be submitted to the Oxford Tropical Research Ethics Committee (OxTREC) and the appropriate local ethics committees for written approval.

The Investigator will submit and, where necessary, obtain approval from the above parties for all substantial amendments to the original approved documents.

12.4 Risks

This study will use drugs that have been studied thoroughly and their toxicities are well described. In general, they are all well tolerated. In the event of any serious or severe adverse event participants will be referred to the local Referral Hospital where best available care will be provided.

12.4.1 Risks of artemether-lumefantrine

The safety of artemether and lumefantrine for treatment of malaria has been evaluated in clinical trials and, post licensing, widespread use for treating malaria in hundreds of millions of patients per year. Reported AL side effects have generally been mild. Reported adverse reactions in clinical trials have been similar or lower in frequency and magnitude to other ACTs. The commonest (>=3%) reported adverse events in clinical studies with AL in adults were headache, anorexia, dizziness and asthenia. AL is not known to cause harmful prolongation of the QTc interval.[22].

12.4.2 Risks of multivitamin

The main side-effects of multivitamin are upset stomach, unpleasant taste or headache which are mild to moderate in nature. Very rarely, these may cause an allergic reaction.

12.4.3 Risk of phlebotomy & finger stick

The primary risks of phlebotomy include local discomfort, occasional bleeding or bruising of the skin at the site of needle puncture, and rarely haematoma or infection. Phlebotomy will be performed by suitably qualified and trained staff using appropriate hygiene measures including gloves and alcohol swabs to clean the skin.

12.4.4 Risk of GPS data

Due to the potential unique nature of the GPS tracking data, it may be possible to identify individuals from their tracks. This will be minimized by the GPS tracking data being kept separately from any personally identifiable information and linked to the data collected on the study CRF only through a unique study code. The GPS tracking data will also be stored anonymously on the tracking device during collection and moved to an encrypted hard drive upon completion of collection.

12.5 Benefits

There are no anticipated direct benefits to the participants in this study. However, knowledge gained from this study is expected to help to assess the efficacy and feasibility of prophylaxis to prevent malaria in forest workers, and to predict its efficacy in reducing overall transmission. The proposed study is a critical step for future use of chemoprophylaxis to protect forest workers in the GMS against malaria.

12.6 Alternatives to Study Participation

Participants are able to decline freely participation in this study. If so, they will receive standard care for their malaria (if applicable).

12.7 Incentives & Compensation

Study participants will be compensated for time lost from work as a result of trial activities, the cost of local transport to attend for the follow up visits and will receive a per diem to cover the costs of meals on those days. The amounts in monetary terms will be determined by CNM in accordance with local norms.

The study will pay for treatment for drug-related SAEs or other research-related injuries. The study cannot pay for long term care for disability resulting from complications of the illness.

12.8 Confidentiality

The trial staff will ensure that the participants' anonymity is maintained. The participants will be identified only by initials and a study number on the CRF and electronic databases. All documents will be stored securely and be accessible to trial staff and authorised personnel only.

13 SAMPLE SHARING AND STORAGE

Samples collected will be used for the purpose of this study as stated in the protocol and stored for future use no longer than 10 years. Consent will be obtained from participants for sample storage and/or shipment of specific samples to collaborating institutions for investigations that cannot be performed locally. Any proposed plans to use samples other than for those investigations detailed in this protocol will be submitted to the relevant ethics committees prior to any testing. Material transfer agreements will be arranged and signed where appropriate/needed.

14 DATA HANDLING AND RECORD KEEPING

Study data will be recorded on Case Report Forms (CRF) at the study sites and stored in a secure database. Validation checks will be built into the study database to identify missing values, inconsistencies, or invalid data. Additionally, study data will be profiled using statistical software to check for outliers and errors not detected by the database. All tasks related to data management will be carried out in accordance with the study data management plan.

Data sharing

With participant's consent, participant's data and results from blood analyses may be shared with other researchers in the future, in an anonymized form.

